6.10 Missing Data Handling

For responder analyses, the last available post-baseline value will be used for patients who do not have an assessment on Day 15. No other data will be imputed.

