Subjects will be both men and women, ages 18-60 years old, with a concussion resulting from a direct or indirect blow, rotation, or whiplash injury to the head or body. For the purposes of this study, we will define diagnosis of concussion/mTBI as those who have met the criteria set forth in this classification schema [23]:

Severity of Traumatic Brain Injury			
	GCS	PTA	LOC
Mild	13-15	<1 day	0-30 mins
Moderate	9-12	>1 to < 7 days	>30 mins to < 24 hrs
Severe	< 9	> 7 days	> 24 hrs

*GCS=Glasgow Coma Scale; PTA=Post-Traumatic Amnesia; LOC=Loss of Consciousness

However, as noted by the American Congress of Rehabilitation Medicine's statement on the definition of mTBI, "Due to the lack of medical emergency, or the realities of certain medical systems, some patients may not have the above factors medically documented in the acute stage. In such cases, it is appropriate to consider symptomatology that, when linked to a traumatic head injury, can suggest the existence of a mild traumatic brain injury [24]. When available, the study team will use medical records to confirm a patient's injury as an mTBI according to the schema above, however, if no records exist or are obtainable, clinical history and symptomatology will be used to confirm the diagnosis.

In Part A, subjects must be consented \leq 28 days post injury. In Part B, subjects must be consented, randomized, and start treatment within 24 hours of presentation to the Trauma Unit.

Subjects in both Part A and B will have a symptom severity score of ≥ 20 at the time of randomization in order to reduce the expected degree (number and severity) of spontaneous symptom resolution prior to study completion.

Subjects with pre-existing neurologic conditions other than mTBI (including cognitive dysfunction) will be excluded.

Subjects with concurrent long bone fractures or orbital fractures will be excluded.

Subjects receiving, or planning to receive, a continuous ketamine infusion while enrolled in study will be excluded.

Subjects with these known endocrinological abnormalities at baseline will be excluded from study: diabetes mellitus, excess or deficiency of growth hormone, cortisol, or prolactin. Exclusion from study for any other endocrinological abnormalities or diagnoses existing at baseline are ultimately up to the discretion of the study physician.

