5.1 Primary Efficacy Outcome Measures

- PCSS severity responder as defined by $\geq 20\%$ improvement over baseline at Day 15 in the severity score
- PCSS symptom responder as defined by $\geq 20\%$ improvement over baseline at Day 15 in the number of symptoms
- PCSS 4MBS responder as defined by $\geq 20\%$ improvement over baseline at Day 15 in the 4MBS severity score
- Change from baseline in PCSS severity score at each post-baseline assessment (Days 4, 8, 11, 15, 21 and 44)
- Change from baseline in PCSS number of symptoms at each post-baseline assessment (Days 4, 8, 11, 15, 21 and 44)
- Change from baseline in PCSS 4MBS severity score at each post-baseline assessment (Days 4, 8, 11, 15, 21 and 44)

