6.2 Analysis Sets

The intent-to-treat (ITT) analysis set is defined as all randomized subjects. This analysis set will be used for demographics and baseline characteristics, entrance criteria violations and other protocol deviations, study drug exposure and prior/concomitant medications summaries.

Since this is an exploratory study being conducted for the purpose of signal detection, the per protocol (PP) analysis set will be used for all efficacy summaries. This set is defined as all patients who completed at least 10 doses) of treatment, had a Day 8 PCSS assessment and no major protocol deviations.

The safety analysis set is defined as all subjects who received at least one dose of study drug. This analysis set will be used for all safety summaries, and subjects will be included in the treatment group which represents the treatment actually administered. If there are no errors in dosing (ie, each subject received the treatment to which he/she was randomized), it is anticipated that the safety analysis set will be the same as the ITT analysis set because it is expected that all randomized subjects will be dosed.

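### A missing Day 15 responder status takes the last available score, with no cut-off at Day 15 and no sensitivity analysis, so the responder rate may be biased in either direction

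*SAP*

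**What the plan says.** The first three primary efficacy measures in SAP 5.1 are responder outcomes: at least 20% "improvement over baseline at Day 15 in the severity score", and the same threshold for the number of symptoms and for the four most bothersome symptoms. SAP 5.1 places post-baseline PCSS assessments on Days 4, 8, 11, 15, 21 and 44, so two of them fall after Day 15.

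SAP 6.10 gives one rule for gaps in the responder analyses: "the last available post-baseline value will be used for patients who do not have an assessment on Day 15". It then adds "No other data will be imputed". No sensitivity analysis of this rule appears elsewhere in the SAP.

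SAP 6.2 states that "the per protocol (PP) analysis set will be used for all efficacy summaries". To be in that set a patient must have taken at least 10 doses, and must have "had a Day 8 PCSS assessment and no major protocol deviations".

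The protocol (Inclusion/Exclusion) requires a symptom severity score of at least 20 "in order to reduce the expected degree (number and severity) of spontaneous symptom resolution prior to study completion". The entry score is there to lessen untreated recovery; it does not remove it.

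**The concern.** Carrying a Day 8 or Day 11 score to Day 15 treats the patient as if recovery stopped at the last contact. In a condition that tends to improve by itself, that is a strong assumption. The rule also does not say that the carried value must come before Day 15. Read literally, a patient who misses only the Day 15 visit is classified on a Day 21 or Day 44 score, after treatment has ended and with more time to recover.

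The responder proportion is the protocol's stated primary objective (Statistical Analysis). The study exists to supply sample size estimates, power calculations and endpoint definitions for later trials (SAP 4 and 6.1), and the ROC analysis of the responder threshold (SAP 6.8) may use the same filled values. If missing data differ between arms in amount, timing or reason, part of the responder difference handed to Phase 2 planning would come from the filling rule. Continuous Day 15 changes are not imputed, so responder and continuous summaries at the same visit can also rest on different patients.

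**Working it through.** The documents give no attrition rate, responder rate or power figure on this point, so there is no planned figure to reproduce. All rates below are assumptions.

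**Who is affected.** Treatment is twice daily for 14 days, 28 doses in all. Ten doses are reached by Day 5 (10/2). Because a Day 8 PCSS is required, losses before Day 8 leave the efficacy set and are not carried forward. A carried value can therefore come from Day 8 or 11, or, read literally, from Day 21 or 44.

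**Inputs.**
- *m*, the share of an arm's per-protocol set with no Day 15 score: assumed 5% to 33%. As a guide to the top of the range, the protocol (General study design) allows 10 replacements for 20 completers in Part A Arm 1, 10/30 = 33%, and 50 enrolled for 40 completers in Part B, 10/50 = 20%. These are ceilings on non-completion if targets are met.
- *g*, the responder rate at Day 15 minus the rate at the carried visit, among the patients with missing data: assumed 5 to 30 points.

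**One arm.** Shift = m × (p_carried − p_15) = −m × g, in percentage points:

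| m | g = 5 | g = 10 | g = 20 | g = 30 |
|---|---|---|---|---|
| 5% | −0.3 | −0.5 | −1.0 | −1.5 |
| 10% | −0.5 | −1.0 | −2.0 | −3.0 |
| 20% | −1.0 | −2.0 | −4.0 | −6.0 |
| 33% | −1.7 | −3.3 | −6.7 | −10.0 |

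**Between arms.** With the same gap in both arms, the bias is (m1 − m2) × g against the arm with more missing data: 10% against 5%, 0.3 to 1.5 points; 20% against 0%, 1.0 to 6.0; 33% against 0%, 1.7 to 10.0; equal shares, 0. With unequal gaps the ordering can flip: 10% × 30 = 3.0 points, but 20% × 10 = 2.0.

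**Direction.** A simulation with assumed exponential recovery at four rates, baseline PCSS of at least 20 and missingness unrelated to outcome gives, at m = 20%:
- Day 8 carried: −1.9 to −4.5 points.
- Day 11 carried: −0.6 to −2.1 points.
- Day 44 used: +0.6 to +4.1 points.
- Day 21 used: +0.3 to +1.8 points. In the slowest recovery scenario the responder rates are 65.1% at Day 21 and 55.9% at Day 15, and 0.20 × 9.2 = 1.8. In the fastest they are 95.3% and 93.6%, and 0.20 × 1.7 = 0.3.

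If lost patients worsen, say 60% responders at Day 8 and 30% at Day 15, the shift is 0.10 × 30 = +3.0 points at m = 10% and 0.20 × 30 = +6.0 at m = 20%.

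**Comparing rules.** Suppose both arms truly respond at 65% on Day 15 and 45% at the carried visit, with 20% and 5% missing. The true difference is 0.
- Carry-forward: 0.20 × (−20) − 0.05 × (−20) = −3.0 points.
- Missing as non-responder: −0.20 × 65 + 0.05 × 65 = −9.75 points.
- Observed Day 15 only: 0, if missingness is unrelated to outcome.

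**What a table would show.** Take 25 in the set, 5 without Day 15, and 14 of 20 observed responders. The rate is 14/20 = 70% observed only, 14/25 = 56% with missing as non-responder, 16/25 = 64% if 2 of the 5 carried scores respond, and 19/25 = 76% if all 5 do.

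**Scale.** At an assumed 70% response, the 95% half-width for a difference is 1.96 × √(2 × 0.7 × 0.3/20) = 28 points with 20 per arm, and 25 points with 25 per arm.

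**The case against.** The strongest reply is that this is a descriptive, unpowered pilot and the likely shift is far inside its sampling error. That stands, and it limits how much weight the point can bear.

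A second reply is that the planned report already exposes much of the problem. SAP 6.3 tabulates completion, analysis-set membership and reasons for not completing by group. SAP 6.1 reports numbers of observations. The Day 15 change summaries (SAP 5.1 and 6.8) use observed data only, so comparing their n with the responder denominator shows how many statuses were filled. SAP 5.3 also leaves room for responder rates on other days. This stands too. What remains unplanned is the source visit of the filled values, an observed-only Day 15 responder rate and a bound.

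A reader might infer that carry-forward understates response, and does so more in the arm with more dropout. The documents do not support that. The sign depends on what happens to patients after loss and on which visit supplies the value, and the size depends on the missing share times the remaining gap, not on dropout alone. The per-protocol set also removes losses before Day 8, so arm-level dropout overstates the share carried.

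A reader might also infer that self-injection against no treatment makes unequal dropout likely in Part A. It is plausible, but the protocol (Attrition) says there are no prior data from which to estimate attrition, and untreated controls could equally leave. SAP version 1.0 still describes a placebo-controlled Part A, and a 10-dose minimum cannot define a per-protocol set for an untreated arm. That is a separate matter, to be settled before the rule can be applied to that comparison.

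**Conclusion.** The point holds as a possible bias of uncertain direction in the first-listed primary outcomes. A patient can qualify for the efficacy set and have no Day 15 score; the rule then supplies a value from another visit, earlier or later, and nothing planned tests how far the result depends on it. Downward bias is the more likely direction only where a Day 8 or Day 11 score is carried while recovery continues.

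The size of about 0.3 to 10 points in one arm rests wholly on the assumed missing shares and gaps, and on missingness unrelated to outcome; the upper end needs a third of the set missing and a 30-point gap. No stated figure in the plan is wrong. The case for acting is that the rule as worded leaves the source visit open and the repair is cheap, not that the pilot's conclusions are at serious risk.

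**What to change.** - In SAP 6.10, restrict carried values to post-baseline assessments on or before Day 15, applied after the visit windows in SAP 6.11.
- For each of the three responder outcomes, add the rate among patients with an observed Day 15 assessment.
- Show missing as non-responder as a conservative bound only. The comparison of rules above shows that it can be further from the truth than carry-forward, so it should not be presented as a less biased estimate.
- Report, by arm, the number of statuses carried forward and the visit each came from.

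No new data or modelling is needed. The cost is a few extra rows in the responder tables, and responder rates that appear as a range when Day 15 data are missing.

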In the event that subjects are enrolled by the Trauma team into Part B while having an inpatient status at TUKHS, the study team, Investigational Pharmacy, and the medical team will work together to dispense, store, and administer the study medication. The study team will continue to work with the Investigational Pharmacy and medical team, as appropriate, for the duration of the subject's inpatient status while on study, as necessary to comply with this protocol.

Attrition: This is a pilot study and no previous data exists as a basis to estimate attrition for this study. Any study participant who withdraws consent or is removed from Part A or Part B of the study during the 28-day trial period or does not successfully complete the protocol required 14 days of dosing may be replaced to allow for 40 subjects who complete the protocol.

Target Duration: The target duration of the treatment intervention with OXE-103 will be two weeks. The total involvement in the study including screening and follow up assessments will be 8 weeks.

Adverse Events: Oxeia, the supplier to the study team of the OXE-103 and placebo, performs and submits safety reports to the FDA under a separate IND. As OXE-103 has already undergone safety testing and the safety profile is known, the adverse events associated with OXE-103 are included in an Investigator's Brochure written by Oxeia Biopharmaceuticals. For the purposes of this study, the study team will collect all adverse events reported by subjects including SAEs and TEAEs regardless of suspected causality, and in accordance with appropriate rules and regulations. Study team will report any that are deemed by Investigator to be:

- Unexpected AND related
- Expected but occurring at an increased frequency or severity
- Occurring in such a way that changes the risks/benefit ratio to study participants and warrants an update in consent form and/or protocol.
- All SAE's will be reported per applicable rules and regulations (IRB/FDA)

Depression Screening: The study team will administer the PHQ-9 questionnaire at specified timepoints to help identify any potential risk or need for intervention.

Safety Monitoring: Subjects participating in Part A Arm 2 (non-treatment control) will not require safety monitoring. All other subjects participating in Part A Arm 1 and Part B Arms 1 & 2 will require safety monitoring.

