Outcomes for the investigation of the effect of OXE-103 will be based on self-reported symptom scoring, quality of life questionnaires, computerized cognitive testing assessing executive function, memory and processing speed, and accelerometer-based balance scoring. Safety assessments will include collection of adverse events, clinical laboratory samples, electrocardiograms (ECGs), vital signs including body weights, suicide screening and physical/neurological examination findings.

3. Study Objectives

The primary objective of this study is to describe the change in symptom burden of subacute or acute concussion for the two treatment groups in each part, as measured by the change from baseline to Day 15 in the Post-Concussion Symptom Score questionnaire (PCSS) total score, total number of symptoms and total score for the 4 most bothersome symptoms (4MBS, as identified on Day 1). Improvements of $\geq 20\%$ will be considered clinically meaningful.

The secondary objectives are to:

- Describe the change in quality of life for the two groups in each part as measured by the change from baseline to Day 15 in the Quality of Life after Brain Injury (QOLIBRI) total score and Patient Global Assessment of Status Visual Analog Scale (PGAS VAS).
- Describe changes in cognitive performance for the two groups in each part as measured by the change from baseline to Day 15 in the BrainCheck composite score.

Exploratory objectives of the study are to:

- Describe the correlation between the change in symptom burden and quality of life during the treatment period for each group in each part.
- Describe changes in symptom burden and quality of life at different time points for the two groups in each part.

4. Sample Size

The exploratory nature of this study is such that it is not powered to yield statistically significant outcomes, but will allow detection of trends within subjects and between groups within each part, will support comparison with standard tests of neurocognitive functions, and will provide sample size estimates for future studies of individuals with acute or persistent concussion related symptoms.

The study will enroll a maximum of 50 subjects in each part, but may stop recruiting if each group has at least 20 participants who have completed the study.

5. Outcome Measures

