6.13 Adjustment for Covariates

No statistical modeling is planned for this exploratory study, therefore, there will be no adjustment for covariates.

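### The Day 15 responder rates and Day 15 mean changes cover different subjects, and the means can be biased if loss after Day 8 depends on improvement

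*SAP*

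**What the plan says.** SAP 3 sets the primary objective as change from baseline to Day 15 in PCSS severity, symptom count and 4MBS. SAP 5.1 serves it with two kinds of primary measure. One is the responder, defined for severity as at least 20% "improvement over baseline at Day 15 in the severity score", with matching definitions for symptom count and 4MBS. The other is change from baseline in the same three scores at each visit, Day 15 included. The secondary measures in SAP 5.2 (QOLIBRI, PGAS, BrainCheck) are all changes from baseline.

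SAP 6.10 treats the two kinds differently: "For responder analyses, the last available post-baseline value will be used for patients who do not have an assessment on Day 15". It then closes with "No other data will be imputed". SAP 6.1 and 6.8 summarise continuous changes by simple descriptives per visit, with a graph of means and 95% confidence intervals. SAP 6.13 adds: "No statistical modeling is planned for this exploratory study".

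All efficacy summaries use the per-protocol set (SAP 6.2): at least 10 doses "of treatment, had a Day 8 PCSS assessment and no major protocol deviations". A Day 15 score is not required.

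On attrition, the protocol says that no earlier data exist to estimate it, and that a subject who withdraws, is removed, or "does not successfully complete the protocol required 14 days of dosing may be replaced".

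**The concern.** A subject can satisfy the per-protocol definition, leave between Day 8 and Day 15, and then be counted in one Day 15 primary result and not in the other. The responder rate describes the whole set, with some early scores standing in for Day 15. The mean change describes only those who were still assessed at Day 15.

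If leaving depends on improvement, the observed-case mean is shifted. It is too favourable when poor improvers leave and too unfavourable when recovered subjects stop attending. No hypothesis test is at stake. What is at stake is the output the pilot exists to give: the means and SDs that SAP 4 and 6.1 intend for later sample-size and power work, the figure showing both arms over time, and any Day 15 correlation of PCSS change with quality of life.

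**Working it through.** The documents give no SD, effect size or dropout rate for this point, so there is no figure of the plan to reproduce.

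**1. Who is affected.** Reading SAP 6.2, 6.10 and 6.11 together:

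| Subject | Day 15 responder rate | Day 15 mean change |
|---|---|---|
| Fewer than 10 doses, or no Day 8 PCSS | not in the set | not in the set |
| In the set, stops drug, still scored at Day 15 | counted | counted |
| In the set, last score on Day 14 | counted as Day 15 (nearest-day rule) | counted |
| In the set, no Day 15 score | counted, last value used | absent |

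Only the last row creates the mismatch. Ten doses out of 2 x 14 = 28 is 5 days of twice-daily dosing, so the dose rule does not close the gap.

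**2. How many.** The protocol makes room for 10 of 30 (33%) non-completers in Part A Arm 1 and 10 of 50 (20%) in Part B. These allowances cover every kind of non-completion, including loss before Day 8 and loss after Day 15. They bound the share in the last row from above and do not estimate it.

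**3. Formula.** Let f be the share of an arm's analysis set without a Day 15 score, and d the mean Day 15 improvement of those scored minus that of those not scored.
- Bias of one arm's mean = f x d.
- Bias of the arm difference = f(OXE-103) x d(OXE-103) - f(control) x d(control).

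With d = 0.5 SD and f = 20%, one arm is off by 0.20 x 0.5 = 0.10 SD. If both arms share those values, the difference is off by 0.10 - 0.10 = 0. For scale, the SE of a difference with 20 per arm is sqrt(2/20) = 0.32 SD.

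**4. Simulated size (all inputs assumed).** 20 per arm; mean Day 15 improvement 15 in control and 23 on OXE-103 (true difference 8); SD 15; adjacent-visit correlation 0.6-0.8. Loss after Day 8 is drawn with weight exp(-k z), where z is standardised Day 8 improvement, so poor improvers leave more often. Overstatement of the observed-case difference:

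| Loss control / OXE-103 | k = 0.25 | k = 0.5 | k = 1.5 |
|---|---|---|---|
| 0 / 10% | about 4% | 5-9% | 14-18% |
| 0 / 20% | 7-9% | 13-16% | 27-37% |

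Repeat runs moved entries by up to about three percentage points. Rounded, this is roughly 4-15% under mild selection (k = 0.25 or 0.5) and 13-35% under strong selection (k = 1.5). The formula agrees: k = 1.5 makes leavers about 11-15 points worse at Day 15, giving 0.10 x 11 = 1.1 points (14% of 8) up to 0.20 x 15 = 3.0 points (38%).

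With 20% loss in both arms and k = 1.5, the difference stays at 8.0, but each arm's own improvement is overstated by about 2-3 points.

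The sampling SD of the difference is 15 x sqrt(1/20 + 1/20) = 4.7 with no loss and 15 x sqrt(1/20 + 1/16) = 5.0 with 4 of 20 lost from one arm.

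A likelihood estimate that also uses the Day 4 and Day 8 scores gave 7.9-8.1 under k = 1.5, with about the same standard error.

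**5. The two primary summaries can disagree.** A separate simulation follows one arm of 25, of whom 5 leave after Day 8. Assumed: baseline mean about 45 with a floor of 20, and average improvement 25% at Day 8 and 40% at Day 15. The 5 leavers are those with the most extreme Day 8 change, which is a severe case.

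| Who leaves | Observed-case mean change | Responders, last value carried | Responders, observed cases |
|---|---|---|---|
| Nobody | -18.2 | 77% | 77% |
| 5 least improved | -21.4 | 70% | 87% |
| 5 most improved | -14.0 | 78% | 72% |

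When the least improved leave, the mean looks better than the truth while the carried-forward responder rate looks worse. On observed cases both move the same way, so at least they can be read together.

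**The case against.** The study is an unpowered descriptive pilot that deliberately avoids modelling. SAP 6.1 already reports the number of observations with each mean, and SAP 6.3 reports completion and reasons for non-completion by group, so a reader can see the shrinking denominator. The affected group may be one or two subjects per arm. Even the larger simulated biases of 2-3 points are smaller than the sampling SD of about 5. The likelihood estimate looks clean because loss was generated from Day 8 scores alone, which builds in missing at random. An unstructured covariance over six visits has 6 x 7 / 2 = 21 parameters, which is a lot for about 20 per arm.

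All of this stands, and it limits the point to a modest improvement. It does not remove the mismatch: showing n reveals the gap but does not correct the mean or the SD.

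A reader might go further in three ways that the documents do not support.
- **All early leavers are in the responder rate but missing from the mean.** Those without 10 doses or a Day 8 PCSS are in neither. A leaver after Day 8 still contributes to the earlier visit means.
- **Part A will lose up to a third of Arm 1, one-sidedly, because only that arm injects.** The third is a replacement allowance, and nothing says that a subject who stops injecting stops being assessed. SAP 1.0 also describes a placebo-controlled Part A; under protocol amendment 1.7 the untreated arm cannot meet the 10-dose rule at all. That is a separate discrepancy.
- **The arm difference is biased in favour of OXE-103.** The sign depends on who leaves, and equal loss leaves the difference unbiased.

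**Conclusion.** The point holds in limited form. For per-protocol subjects without a Day 15 score, the SAP counts them in the Day 15 responder rate and omits them from the Day 15 mean change, so two primary results at the same time point describe different subjects. Bias in the means and SDs is possible, not shown. It needs loss after Day 8 to depend on improvement and, for the arm difference, to differ between arms.

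Under the assumed values, the arm difference of 8 is overstated by roughly 4-15% (mild selection) or 13-35% (strong selection) when 10-20% of the OXE-103 arm alone is lost. The overstatement is zero with equal loss and reverses if recovered subjects are the ones lost. The percentages scale with the assumed difference and selection strength, and the true share lost is unknown. This is a worthwhile, cheap improvement and does not invalidate the planned summaries.

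**What to change.** Keep the planned observed-case descriptive tables as they are, and make three changes to the SAP.

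- **6.8 and 6.10:** for the Day 15 changes in PCSS severity, symptom count, 4MBS, QOLIBRI, PGAS and BrainCheck, add a likelihood-based repeated-measures estimate by part. It uses baseline and all observed post-baseline scores, with arm, visit and arm-by-visit terms. Prespecify a simpler covariance structure in case the unstructured one does not converge.
- **6.13:** amend the sentence on modelling to allow this.
- **6.8:** beside the carried-forward responder rate, report the Day 15 responder rate on observed cases, so that responder rate and mean change are shown on the same subjects.

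The cost is SAP wording and one standard SAS procedure per outcome, with no new data or visits. The downside is a missing-at-random assumption and one added model per outcome in a descriptive pilot. The observed-case responder rate makes the two results comparable but does not itself remove selection.
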